6.3. Analysis for Secondary Endpoints

6.3.1. Efficacy Endpoints Analysis

Except ORR for Part 2, efficacy is a secondary objective. The efficacy analysis will be performed in the mITT population. Part 1 and Part 2 data will be summarized separately, and may also be pooled together for analysis if deemed necessary. Efficacy data assessed by RECIST will be analyzed separately from those assessed by irRECIST.

Tumor response data in Part 1, Part 2 and across the two Parts may be summarized with descriptive statistics (frequency and percentage) in the following groups by visit and then best overall response across all visits:

- Overall summary for all doses and all tumor types;
- By tumor type regardless of dose;
- By dose regardless of tumor type;
- By dose and tumor type if data permit.

Summary tables of best overall response rate, PFS, OS, DOSD, and DOR may be provided by the groups aforementioned when deemed necessary (e.g. if there are ≥ 5 patients in a specific group).

Efficacy listings (tumor measurements listings and tumor response listings) will be provided that include the investigator provided tumor measurement data, tumor response, best overall response, first CR/PR date, last date with CR or PR, most recent date without progression, progression date, death date, and last tumor assessment date, etc.

Swimmer plot for individual clinical response and time on treatment, waterfall plot for individual tumor size percent change from baseline, and spider plot for individual tumor size percent change from baseline over time will be presented for RECIST and irRECIST separately.

The following table provides an overview of the efficacy analysis.

Endpoint	Analysis Set	Statistical Method	Model/ Covariates/ Strata	Missing Data
Overall response	mITT	Exact CI	See aforementioned summary descriptions on data pooling across dose and tumor type	Observed case
Overall Survival	ITT	Kaplan-Meier	See aforementioned summary descriptions on data pooling across dose and tumor type	Censored at last visit
Progression Free Survival (PFS)	mITT	Kaplan-Meier	See aforementioned summary descriptions on data pooling 3721 across dose and tumor type	Censored per Appendix 9.2
Time to Progression (TTP) and Time to Response (TTR)	mITT	Kaplan-Meier	See aforementioned summary descriptions on data pooling across dose and tumor type	Censored per Appendix 9.2

Endpoint	Analysis Set	Statistical Method	Model/ Covariates/ Strata	Missing Data
Duration of Response (DOR)	mITT	Kaplan-Meier	See aforementioned summary descriptions on data pooling across dose and tumor type	Censored per Appendix 9.2
Duration of Stable Disease (DOSD)	mITT	Kaplan-Meier	See aforementioned summary descriptions on data pooling across dose and tumor type	Censored per Appendix 9.2

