3.2. Secondary Endpoint(s)

Part 1:

- PK parameters of PF-06801591: Cycle 1 and Cycle 4 C_{max} , area under the concentration versus time curve (AUC) from time zero to the last quantifiable time point prior to the next dose (AUC_{last}), and if data permit, CL, V_d , volume of distribution at steady state (V_{ss}), accumulation ratio (Rac) when feasible, and terminal elimination $t_{1/2}$.
- Incidence of anti-drug antibodies (ADA) and neutralizing antibodies (NAb) against PF-06801591.
- PD-1 receptor occupancy (RO) by PF-06801591, as assessed by measuring the levels of unbound (free) cell surface PD-1 on circulating T cells over time following PF-06801591 administration.
- Objective tumor response, as assessed using the Response Evaluation Criteria in Solid Tumor (RECIST) version 1.1 and immune-related RECIST (irRECIST); and proportion of subjects with PR (and irPR, as appropriate).
- Time-to-event endpoints based on RECIST and irRECIST and PFS (and irPFS as appropriate), Duration of stable disease (DOSD, or irDOSD as appropriate), and Duration of response (DOR, or irDOR as appropriate).
 - PFS is defined as the time from treatment start date to date of first documentation of progression or death due to any cause.
 - Duration of stable disease is defined from the start of the treatment until the criteria for progression are met, taking as reference the smallest tumor measurements recorded since the treatment started, including the baseline measurements. This endpoint is applicable to the subset of patients who achieved a best overall response of stable disease (SD), those patients whose best overall response is not SD will be excluded from this endpoint analysis. A minimum of 6 weeks (with a - 5 days window, which is essentially a minimum of 35 days) interval of two assessments is required for this endpoint.
 - Duration of response is defined as the time from start date (which is the date of first documentation of PR or CR) to date of first documentation of objective progression or death. DOR is only applicable to those patients with an objective response.

Part 2:

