- Time to event endpoints by PF-06801591 administered by SC based on RECIST and irRECIST, including time to response (TTR) and time to progression (TTP) as well as PFS (and irPFS as appropriate), DOSD (and irDOSD as appropriate), and DOR (and irDOR as appropriate). Time to response is defined as the time from the study treatment date to the first documentation of PR or CR. Time to progression is the time from start date to date of first documentation of objective progression.
- *Median time to death, proportion of patients alive at 6 months, 1 year, and 2 years.* Time to death (i.e. overall survival) is the time from treatment start date to date of death due to any cause.
- Trough PF-06801591 concentrations for selected cycles.
- Incidence of ADA and NAb against PF-06801591 administered by SC.

CCI

Detailed descriptions of Endpoints are provided in [Appendice 9.1](#), [9.4](#), and [9.5](#).

CCI

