5.2.3. Sample Size Determination

The exact sample size for the dose escalation design in Part 1 cannot be specified in advance due to the dynamic features of mTPI. For the first dose level (0.5 mg/kg IV), in the absence of actual DLTs, a total of 2 patients will be enrolled: 2 patients in Part 1A and no patient in Part 1B. For subsequent dose levels it is anticipated that approximately 2 to 4 patients will be enrolled in Part 1A and approximately 2 to 5 patients in Part 1B with available pre- and on-treatment biopsies for IHC testing and up to 9 patients at dose levels 1, 3, and 10 mg/kg administered by IV in Part 1. A single cohort with SC administration at a dose level of 300 mg of PF-06801591 will be opened for enrollment shortly after the cohort at a dose level of 3 mg/kg IV in Part 1A will have completed enrollment and the 21-day DLT observation period. This cohort at a dose level of 300 mg SC will seek 2 to 4 patients in Part 1A, up to 11 patients in Part 1B with available pre- and on-treatment biopsies for IHC testing, and up to 15 patients in Part 1. The actual Part 1 sample size may be smaller, depending on the underlying dose toxicity profile, and the number of dose levels studied.

Part 2 of the study will enroll approximately 60 patients with NSCLC who progressed on or were intolerant to systemic therapy or for whom systemic therapy was refused or unavailable and are treatment naïve for anti-PD-1 or anti-PD-L1. NSCLC was selected for historical comparability to prior large anti-PD-1 studies and dosing of 300 mg SC in Part 2 has been selected based on safety, PK, available biomarker data and preliminary anti-tumor activity from Part 1. There is no hypothesis testing in Part 2. Estimation approach is used to characterize the precision of response data. The estimation of ORR using N=60 is described as follows. Suppose that the ORR estimate is 19% in Part 2 with N=60, then the 80% and 90% confidence intervals of the true ORR will be (13.3, 26.3%) and (12.1, 28.6%) respectively. Note that an ORR of 19% was observed in a clinical trial for nivolumab in previously treated NSCLC patients. In Part 2, approximately 40 urothelial cancer patients will also be enrolled, the sample size is based on clinical considerations of expanding the safety database.

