5.3.1. Analyses for Time to Event Data

Time to event endpoints in this study include progression-free survival (PFS), duration of response (DOR), duration of stable disease (DoSD), time to response (TTR), time to progression (TTP), and overall survival (OS). When appropriate and data permits, the immune-response version of these endpoints based on irRECIST will also be explored. The specific definitions of these endpoints are provided in [Section 3](#). These endpoints will be summarized using the Kaplan-Meier method² and displayed graphically when appropriate. Median event times and 2-sided 95% confidence intervals for each time-to-event endpoint (Brookmeyer and Crowley, 1982)³ will be provided.

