9.2. Time to Event Data Analysis Censoring Rules

Table 9.2.1: Progression Free Survival and Duration of Response

Situation	Date of Progression/Censoring¹	Outcome
Inadequate baseline assessment	First dosing date in Cycle 1	Censored
No on-study assessments	First dosing date in Cycle 1	Censored
Alive over the course of the study and no progression	Date of last objective tumor assessment	Censored
Progression or death documented on or between scheduled tumor assessments	Date of first objective tumor assessment showing objective progression or death date	Progressed/Death (Event)
Treatment discontinuation for undocumented progression	Date of last objective tumor assessment	Censored
Treatment discontinuation due to toxicity or other reason	Date of last objective tumor assessment	Censored
Progression/Death prior to second planned tumor	Date of death	Progressed/Death (Event)
Death or progression after 2 or more missed tumor assessments	Date of last objective tumor assessment prior to the event	Censored

1. For date of censorship, if a tumor assessment takes place over a number of days (eg, superficial lesions one day, scans another), the last date is used as the assessment date.
2. The first two reasons (Inadequate baseline assessment; No on-study assessments) are not applicable for Duration of Response, as that endpoint is only for the subset of responders.

Table 9.2.2: Time to Progression

Situation	Date of Progression/Censoring¹	Outcome
Inadequate baseline assessment	First dosing date in Cycle 1	Censored
No on-study assessments	First dosing date in Cycle 1	Censored
Alive over the course of the study and no progression	Date of last objective tumor assessment	Censored
Progression Documented on or between scheduled tumor assessments	Date of first objective tumor assessment showing objective progression	Progressed (Event)
Treatment discontinuation for undocumented progression	Date of last objective tumor assessment	Censored

Situation	Date of Progression/Censoring¹	Outcome
Treatment discontinuation due to toxicity or other reason	Date of last objective tumor assessment	Censored
New anticancer treatment prior to documented progression	Date of last objective tumor assessment prior to new anticancer treatment	Censored
Death prior to first planned tumor assessment	Start date (C1D1)	Censored
Death without objective progression	Date of last objective tumor assessment prior to death	Censored

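### Time to response is planned as a Kaplan-Meier median in mITT with no rule for non-responders; separately, the 35-day stable-disease minimum does not follow from 6 weeks minus 5 days

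*SAP*

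**What the plan says.** **Time to response.**

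- SAP 3.2 defines it for Part 2: "Time to response is defined as the time from the study treatment date to the first documentation of PR or CR". No population is attached. In the same section duration of response (DOR) is restricted, "DOR is only applicable to those patients with an objective response", and duration of stable disease (DOSD) is restricted to patients whose best overall response is stable disease.
- SAP 6.3.1 states "The efficacy analysis will be performed in the mITT population". Its overview table gives TTR the same row as time to progression (TTP), "Time to Progression (TTP) and Time to Response (TTR": mITT, Kaplan-Meier, missing data handled by censoring per Appendix 9.2.
- SAP 5.3.1 lists TTR among the time-to-event endpoints and promises "Median event times and 2-sided 95% confidence intervals for each time-to-event endpoint".
- Appendix 9.2 holds two tables. One covers PFS and DOR; the other is "Table 9.2.2: Time to Progression". Neither mentions TTR.
- SAP 6 asks for TTR in Part 2 with and without confirmation, under both RECIST 1.1 and irRECIST, so the gap affects four versions of the endpoint.
- Protocol 2.2 makes TTR a Part 2 secondary endpoint, and protocol 9.4 also names Kaplan-Meier for it, by tumor type.

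**Planning response rate.** SAP 5.2.3 works its precision example at 19% and explains: "Note that an ORR of 19% was observed in a clinical trial for nivolumab in previously treated NSCLC patients".

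**Stable disease.** SAP 3.2 requires at least 6 weeks between two assessments for DOSD, with a window of minus 5 days, "which is essentially a minimum of 35 days". The Part 2 endpoint list names DOSD again without redefining it.

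**The concern.** Kaplan-Meier with a median suits an event that most patients will have, or would have had if followed longer. Response is not such an event here. Most patients are expected never to respond, and many will progress or die first. What the curve and median mean then depends on how those patients are treated, and the plan's pointer for that leads to tables that do not cover TTR.

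Two programmers could follow the SAP and produce different results. One would report a median that is not reached. The other could report a response curve that ends above the ORR, which is the primary efficacy endpoint of Part 2.

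The stable-disease figure is a separate point: a stated threshold that disagrees with the numbers it is derived from, set in weeks that match the IV scan interval and not the Part 2 one.

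**Working it through.** **1. The plan's own figure, 35 days.** Inputs from SAP 3.2: 6 weeks, window of minus 5 days. 6 × 7 = 42, and 42 − 5 = 37. Shifting the count by one day for a different convention gives 36 or 38. Only a 7-day window gives 35 (42 − 7). The stated figure is not reproduced.

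**2. Expected events.** At an ORR of 19%, 100 − 19 = 81% of NSCLC patients do not respond. Expected responders are 0.19 × 70 = 13.3 at the current protocol's N, or 0.19 × 60 = 11.4 at the SAP's N.

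**3. Rule A: non-responders kept at risk to the end of follow-up.** With nobody censored before the last response, 1 − KM equals responders divided by N, so it levels off at 19%. A median needs half the patients to respond. By the binomial tail at 19%:

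- P(at least 35 of 70) = 5.2 × 10⁻⁹
- P(at least 30 of 60) = 6.3 × 10⁻⁸

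Even at an assumed ORR of 30% these are only 0.0004 and 0.0009. The median is not reached, and nothing is overstated.

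**4. Rule B: non-responders censored at progression, death or last assessment.** The product-limit estimate is 1 − Π(1 − dⱼ/nⱼ), where dⱼ is the number responding at scan j and nⱼ the number still at risk. The splits below are assumptions chosen for illustration; no document gives them. Each has 19 responders among 100 patients.

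| Responses at scans 1/2/3 | Leaving without response at scans 1/2/3 | Calculation | 1 − KM |
|---|---|---|---|
| 12/5/2 | 30/15/10 | 1 − (1 − 12/100)(1 − 5/58)(1 − 2/38) | 23.8% |
| 12/5/2 | 40/20/10 | 1 − (1 − 12/100)(1 − 5/48)(1 − 2/23) | 28.0% |
| 10/6/3 | 45/20/10 | 1 − (1 − 10/100)(1 − 6/45)(1 − 3/19) | 34.3% |

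In the first row, for example, 100 − 12 − 30 = 58 are at risk at scan 2 and 58 − 5 − 15 = 38 at scan 3. Every result exceeds 19%, and none reaches 50%.

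**5. Rule B over a wider range.** This is a simulation of 2,000 trials per scenario with N = 70, ORR 19% and 8-weekly scans. It assumes that 40%, 50% or 60% of remaining non-responders progress per interval. Responses are assumed to fall 60/25/10/5% over scans 1 to 4, or 40/30/15/10/3/2% over scans 1 to 6. Mean final 1 − KM ran from 27% to 67%. The median was reached in 0.4% to 74% of trials, although only 19% of patients respond.

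**6. Reach of the 35-day slip.** The earliest in-window first scan is day 42 − 5 = 37 on the IV schedule and day 56 − 5 = 51 on the subcutaneous schedule. Neither falls below 37, so replacing 35 by 37 reclassifies only intervals of 35 or 36 days.

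**The case against.** **The mITT label may only name the parent set.** The same table labels DOR and DOSD mITT, and both are subsets by definition. This stands in part: the documents leave the TTR population undefined and do not expressly include every mITT patient. But DOR and DOSD each have a restriction in SAP 3.2, and TTR has none.

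**A reader might infer that the plan will certainly inflate the curve, or that the median cannot exist.** Neither is supported as a flat statement. Each depends on the missing rule, and they pull in opposite directions: rule A gives no median and no inflation, while rule B inflates and may then produce a median. Nor does Appendix 9.2 direct censoring at documented progression, which is an event in both of its tables. It censors, among others, treatment discontinuation and, for TTP, death without progression. Carrying that logic over to TTR non-responders is an extrapolation, though an easy one because TTR shares the TTP row.

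**Progression does not always rule out response.** Under irRECIST a response can follow a first, unconfirmed progression, and patients may stay on treatment after it. This stands and shapes the fix.

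**A reader might infer that the subcutaneous stable-disease minimum should be 51 days, or that disease control rate is inflated.** No document ties the minimum to the 8-week interval, and SAP 3.2 attaches it to DOSD only. The best-response table in SAP 9.4 refers to a minimum stable-disease duration but gives no number. Both inferences go beyond the text.

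**The stakes are limited.** Part 2 has no hypothesis test, ORR is reported on its own with exact intervals, first response dates are listed, and a median that is not reached is ordinary output. This limits the seriousness; it does not fill the gap.

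**Conclusion.** The point holds. TTR has no stated population restriction and no rule for non-responders, and the cited appendix does not supply one. The planned median is uninformative under either plausible rule: at an ORR of 19% it is not reached if non-responders stay at risk, and any value reached by censoring them is an artefact.

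Under the second rule the curve ends above the ORR. The direction holds whenever non-responders leave the risk set before later responses occur. The size, about 24% to 34% in the worked splits and wider in simulation, rests on assumed response timing and drop-out. The 19% is an NSCLC planning value; the SAP sets none for urothelial carcinoma.

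The stable-disease threshold is a plain arithmetic error of 2 days with a small effect. Whether the 6-week minimum is meant for Part 2 is a separate open question. No primary conclusion changes, but a secondary endpoint needs a defined analysis.

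**What to change.** **TTR.** Give it its own row in SAP 6.3.1 and choose one of two analyses:

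- *Responders only.* Report median and range, with a footnote that the summary conditions on response. Every patient then has the event and no censoring rule is needed. The base is small, about 13 NSCLC patients at 19% of 70.
- *Cumulative incidence of response in mITT.* Treat progression or death without response as competing events. For irRECIST the progression event should be confirmed irPD. The curve then stays consistent with the ORR.

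In either case, exempt TTR from the Kaplan-Meier median in SAP 5.3.1, and either remove the Appendix 9.2 reference or add a TTR rule there.

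**DOSD.** In SAP 3.2 correct 35 to 37 days, or reconcile the 6-week, 5-day and 35-day figures if another window was meant. State whether the 6-week minimum applies to Part 2, where scans are every 8 weeks.

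**Cost.** SAP wording and minor programming, with no new data. Protocol 9.4 also names Kaplan-Meier for TTR, but both documents let the SAP modify the planned analyses and reserve protocol amendment for major changes to the primary endpoint or its analysis. TTR is secondary, so a SAP amendment is enough.

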6.3.2. Pharmacokinetics Analyses

The concentration-time data of PF-06801591 will be summarized by descriptive statistics (n, mean, standard deviation, coefficient of variation, median, minimum, maximum, and geometric mean) according to dosing cohort and time for each part of the study. In addition, the concentration-time data from Part 2 will also be summarized by descriptive statistics according to tumor type.

The actual time of sample collection will be used in PK parameter calculation. In the event that the actual sampling time is not available, the nominal time may be used if there is no evidence that the actual sampling time deviates substantially from the nominal time.

Presentation of PF-06801591 concentration-time data

The concentration-time data of PF-06801591 will be presented as below:

- a listing of all concentrations by cohort, subject ID and nominal time. The concentration listing will also include the actual times. Deviations from the nominal time will be given in a separate listing.
- a summary of concentrations by cohort and nominal time, where the set of statistics will include n, mean, standard deviation, median, coefficient of variation (cv), minimum, maximum and the number of concentrations above the lower limit of quantification.
- for the concentration-time data after the 1st and 4th dose, median concentration-time plots (on both linear and semi-log scales) against nominal time postdose by cohort (all cohorts on the same plot per scale, based on the summary of concentrations by cohort and time postdose).
- for the concentration-time data after the 1st and 4th dose, mean concentration-time plots (on both linear and semi-log scales) against nominal time postdose by cohort (all cohorts on the same plot per scale, based on the summary of concentrations by cohort and time postdose).

For drug concentration summary statistics, median and mean plots by sampling time, the nominal PK sampling time will be used; for individual subject plots by time, the actual PK sampling time will be used, with the pre-dose time set to zero.

Calculation of PF-06801591 PK parameters

For patients enrolled in Part 1 of the study, the individual concentration-time data of PF-06801591 during Cycle 1 and Cycle 4 will be analyzed separately by non-compartmental methods to estimate the PK parameters. The PK parameters estimated will include C_{max} , T_{max} , and AUC_{last} (AUC_{tau} at steady state). If data permit or if considered appropriate, $t_{1/2}$, CL (or CL/F for SC cohort), V_d (or V_d/F for SC cohort; V_{ss} at steady state), and accumulation ratio (R_{ac}) will also be estimated for Cycle 1 and Cycle 4. For IV cohorts in Part 1, individual Cycle 6 pre-dose concentrations will be used in lieu of Cycle 5 pre-dose concentrations while calculating Cycle 4 PK parameters. The PK parameters will be summarized descriptively by dose level and cycle.

Additionally, for Part 1, dose-normalized AUC_{last} and C_{max} will be plotted against dose (using a logarithmic scale) by cycle. These plots will include individual patient values and the geometric means for each dose. These plots will be used to help understand the relationship between the PK parameters and dose.

For patients enrolled in Part 2 of the study, trough concentrations of PF-06801591 will be summarized descriptively by cycle and by tumor type.

PK parameters will be calculated using standard non-compartmental methods:

Parameter	State	Method of Determination
AUC_{tau}	sd, ss	Linear/Log trapezoidal method
AUC_{last}	sd,ss	Linear/Log trapezoidal method
AUC_{inf}^a	sd	$AUC_{last} + (C_{last}^*/kel)$, where C_{last}^* is the predicted serum concentration at the last quantifiable time point estimated from the log-linear regression analysis.
C_{max}	sd, ss	Observed directly from data
T_{max}	sd, ss	Observed directly from data as time of first occurrence
CL and CL/F	sd, ss	Dose/ AUC_{inf} for sd ^a Dose/ AUC_{tau} for ss
Vd/F	sd, ss	Dose/ AUC_{inf} for sd Dose/(AUC_{tau} / kel) for ss
V_{ss}^a	sd, ss	CL * MRT, where MRT is the mean

		residence time adjusted for the duration of infusion
$t_{1/2}^a$	sd	$\text{Loge}(2)/\text{kel}$, where kel is the terminal phase rate constant calculated by a linear regression of the log-linear concentration time curve.

^a if data permit.

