1.1. Mechanism of Action/Indication

PF-06801591 is a humanized, hinge region-stabilized IgG4 monoclonal antibody (mAb) specific for human PD-1 that can selectively binds to human PD-1 and block the interaction between PD-1 and PD-L1/PD-L2. PF-06801591 has been shown to induce T cell proliferation and interferon gamma (IFN- γ) and other proinflammatory cytokines secretion in human activated CD8⁺ T cells [Figure 3].

PF-06801591 showed similar binding affinity to human PD-1 compared to pembrolizumab and nivolumab.²⁵

The projected half-life ($t_{1/2}$) of approximately 3 weeks for PF-06801591 is similar to that of nivolumab and pembrolizumab.^{2,4}

In this study, PF-06801591 will be used to assess safety and tolerability of increasing dose levels in patients with locally advanced or metastatic melanoma, SCCHN, ovarian cancer, sarcoma, NSCLC, or other solid tumor types with clinical evidence of response to anti PD-1 or PD-L1 agents.

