9.5. Analysis of Pharmacokinetics and Pharmacodynamics

9.5.1. PF-06801591 Pharmacokinetic Analysis

The concentration-time data of PF-06801591 will be summarized by descriptive statistics (n, mean, and standard deviation, coefficient of variation, median, minimum, maximum, and geometric mean) according to dosing cohort and time for each part of the study. In addition, the concentration-time data from Part 2 will also be summarized by descriptive statistics according to tumor type.

For patients enrolled in Part 1 of the study, the individual concentration-time data of PF-06801591 during Cycle 1 and Cycle 4 will be analyzed separately by non-compartmental methods to estimate the PK parameters. The PK parameters estimated will include C_{max} , T_{max} , and AUC_{last} . If data permit or if considered appropriate, $t_{1/2}$, CL, volume of distribution (V_d)/ volume of distribution at steady state (V_{ss}), and accumulation ratio (Rac, when feasible) will also be estimated for Cycle 1 and Cycle 4. The PK parameters will be summarized descriptively by dose level and cycle.

Additionally, for Part 1, dose-normalized AUC_{last} and C_{max} will be plotted against dose (using a logarithmic scale) by cycle. These plots will include individual patient values and the geometric means for each dose. These plots will be used to help understand the relationship between the PK parameters and dose.

For patients enrolled in Part 2 of the study, trough PF-06801591 concentrations will be summarized descriptively by cycle and tumor type.

CCI

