5.4.3. Pharmacokinetics

Concentrations below the limit of quantification

In all data presentations (except listings), concentrations below the limit of quantification (BLQ) will be set to zero. (In listings BLQ values will be reported as “<LLQ”, where LLQ (i.e. lower limit of quantification) will be replaced with the value for the LLQ).

Deviations, missing concentrations and anomalous values

Patients who experience events that may affect their PK (eg, incomplete dosing) may be excluded from the PK analysis.

In summary tables and plots of median profiles, statistics will be calculated with concentrations set to missing if one of the following cases is true:

1. A concentration has been reported as ND (ie, not done) or NS (ie, no sample),
2. A deviation in sampling time is of sufficient concern or a concentration has been flagged anomalous by the pharmacokineticist.

Note that summary statistics will not be presented at a particular time point if more than 50% of the data are missing.

An anomalous concentration value is one that, after verification of bioanalytical validity, is grossly inconsistent with other concentration data from the same individual or from other subjects. For example, a BLQ concentration that is between quantifiable values from the same dose is considered as anomalous. Anomalous concentration values may be excluded from PK analysis at the discretion of the PK analyst.

Pharmacokinetic parameters

Actual PK sampling times will be used in the derivation of PK parameters. If a PK parameter cannot be derived from a subject’s concentration data, the parameter will be coded as NC (ie, not calculated). (Note that NC values will not be generated beyond the day that a subject discontinues).

In summary tables, statistics will not be presented for a particular treatment group if more than 50% of the data are NC. For statistical analyses, PK parameters coded as NC will also be set to missing.

If an individual subject has a known biased estimate of a PK parameter, this will be footnoted in summary tables and will not be included in the calculation of summary statistics or statistical analyses.

CCI

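### Neither Vd/F formula in the SAP's PK parameter table gives a volume: the single-dose entry is clearance and the steady-state entry is clearance times kel

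*SAP*

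**What the plan says.** SAP 6.3.2 introduces its parameter table with the statement "PK parameters will be calculated using standard non-compartmental methods". The rows that matter here are:

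- **CL and CL/F:** Dose/AUCinf for single dose, Dose/AUCtau for steady state.
- **Vd/F:** Dose/AUCinf for single dose, then "Dose/(AUC_{tau} / kel) for ss".
- **t1/2:** loge(2)/kel, "where kel is the terminal phase rate constant calculated by a linear regression of the log-linear concentration time curve". This row is marked single dose only.

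The text above the table plans Vd/F for the SC cohort in Cycle 1 and Cycle 4, so the row is in use. Volume of distribution is among the Part 1 secondary PK endpoints (Protocol 2.1, SAP 3.2). Protocol 9.5.1 names the volume parameters under the condition "If data permit or if considered appropriate" but gives no formula. SAP 5.4.3 adds that "statistics will not be presented for a particular treatment group if more than 50% of the data are NC", where NC means not calculated. SAP 5.2.3 caps the 300 mg SC cohort: "and up to 15 patients in Part 1".

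**The concern.** One expression cannot define both clearance and volume, yet the single-dose entries for CL/F and Vd/F are identical. The steady-state entry does contain kel, but it divides the AUC by kel inside the parentheses where it should multiply. The row therefore contradicts its own lead-in about standard methods.

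Programmed literally, the SC cohort's Vd/F table would report clearance under a volume label in Cycle 1 and a quantity with no volume meaning in Cycle 4, and the two cycles could not be compared. If the PK software applied its own definition instead, the report would depart from the SAP without explanation.

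Three smaller gaps sit in the same row. It lacks the footnote on data sufficiency that AUCinf, single-dose CL, Vss and t1/2 carry. It needs a kel at steady state although kel is defined only in a row marked single dose. The text also lists Vd for the IV cohorts, but no row carries that label.

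**Working it through.** The SAP gives no numerical value for Vd/F to reproduce, so the check is algebra and units, followed by an illustration.

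**Algebra.** kel has unit 1/time and AUC has unit (mass/volume) × time.

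- Single dose as printed: Dose/AUCinf = CL/F. Unit: volume/time.
- Steady state as printed: Dose/(AUCtau/kel) = (Dose/AUCtau) × kel = CL/F × kel. Unit: volume/time².
- Terminal volume: (CL/F)/kel = Dose/(AUC × kel). Unit: volume.

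Reading the steady-state entry as (Dose/AUCtau)/kel would give a volume, but the printed parentheses exclude it.

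**Inputs for the illustration.**

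- Dose 300 mg every 28 days (Part 1 SC schedule).
- Half-life 21 days, from the projection in Protocol 1.1 ("of approximately 3 weeks for PF-06801591 is similar to that of nivolumab and pembrolizumab"), so kel = ln 2/21 = 0.0330 per day.
- V/F is not in the documents. Assumed values are 5 L, and 6.67, 10.0 and 13.33 L. The last three are V = 4, 6 and 8 L divided by the 60% bioavailability assumed in Protocol 1.6.
- One-compartment model with first-order absorption, in which AUCinf equals AUCtau at steady state. The assumed absorption rate constant (0.25 per day for 5 L, 0.3 per day for the others) does not affect either AUC.

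| Assumed V/F (L) | AUC = Dose/(CL/F) (mg·day/L) | Printed single dose (L/day) | Printed steady state (L/day²) | Dose/(AUC × kel) (L) |
|---|---|---|---|---|
| 5.00 | 1817.8 | 0.165 | 0.0054 | 5.00 |
| 6.67 | 1363.3 | 0.220 | 0.0073 | 6.67 |
| 10.00 | 908.9 | 0.330 | 0.0109 | 10.00 |
| 13.33 | 681.7 | 0.440 | 0.0145 | 13.33 |

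First row in full: 300/1817.8 = 0.165; 300/(1817.8/0.0330) = 0.0054; 300/(1817.8 × 0.0330) = 5.0.

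The printed entries are kel times and kel² times the true volume (0.0330 and 0.00109 with time in days). These factors change with the time unit. In hours kel is 0.001375, and the 10 L case gives 0.01375 L/h and 0.0000189 L/h².

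**How often the single-dose entry can be computed.** A 28-day cycle covers 28/21 = 1.33 half-lives. The share of AUCinf beyond day 28 is 2^(−28/21) = 40% for a mono-exponential decline, and 46% in the absorption model with rate constant 0.25 per day. AUCinf may therefore be set to NC for many patients in Cycle 1, and the rule in SAP 5.4.3 could then suppress that summary.

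**The case against.** The strongest objection is that the table was read from extracted PDF text, and mathematics elsewhere in the SAP text looks unreliable. SAP 6.6 shows the Fridericia correction with a fifth root, where Protocol 9.6.3 shows a cube root. The single-dose entry could be a repeated line, and the steady-state entry differs from a correct one by a single symbol. That possibility stands and is why the PDF should be opened first. It is not a likely explanation: two different misreads in one cell would be needed, while operators in neighbouring rows (the product in Vss, the division by kel in AUCinf) came through intact.

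Other objections narrow the point without removing it:

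- The text above the table already makes these parameters conditional on the data, so the missing footnote mark is cosmetic.
- Cycles 1 and 4 are analysed separately and t1/2 is listed for both, so each cycle's own kel is the natural reading. Only the single-dose label on the t1/2 row is then out of line.
- The row is labelled Vd/F, which the text assigns to SC, and Vss gives IV patients a volume. Extending the error to IV is conditional. The IV caps add to 2 + 3 × 9 = 29, but 29 + 15 = 44 exceeds the Part 1 total of about 40, so 29 is a ceiling and not an expected count.
- A volume reported in L/day would probably be noticed, and standard software may use its own correct definition. This lowers the chance of a wrong table but leaves the SAP text wrong.

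**Conclusion.** The point holds. As printed, both Vd/F entries define something other than a volume, and this follows from the SAP's own definitions whatever values are assumed for V/F or absorption. The numerical sizes do depend on the assumed V/F and the projected half-life.

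The consequence is minor. It concerns one secondary, descriptive parameter in the Part 1 SC cohort of up to 15 patients, extending to IV only if the row is meant to serve IV as well. AUC, Cmax, CL, CL/F, Vss and t1/2 are unaffected. No dose decision, primary endpoint or patient is affected, and a correct Vd/F can be recovered afterwards as (CL/F)/kel. The remaining uncertainty is whether the source PDF prints the row as extracted.

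**What to change.** Check the row in the source PDF. If it reads as above, replace it with:

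- single dose: Vd/F = Dose/(AUCinf × kel)
- steady state: Vd/F = Dose/(AUCtau × kel)

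Give the unit as volume and add the same data-sufficiency footnote that AUCinf carries. In the same edit, state which cycle's kel the steady-state entry uses and whether the row also serves Vd for the IV cohorts.

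The cost is one table row, one footnote mark and a sentence of clarification. Data collection, sampling and design do not change.
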